The study is designed as a prospective, controlled multi-center study including sites from Korea, Japan and Mexico.

To achieve all the primary objectives, the study will include 2 subgroups. The relationship between the two subgroups is illustrated in the following table and graph:

Subgroup	Objectives	Trial Group	Control Group	Design	Endpoint(s)
2	Compare early ROM, Clinical Outcomes, assess Kinetic and Kinematic characteristics between Vanguard Complete Knee System and Vanguard High Flex Rotating Platform Knee System*	Vanguard Complete Knee System w/ std tray (part of subgroup 1 control)	Vanguard High Flex RP (Current Design)	RCT	ROM, AKS,.
4**	Compare early ROM, clinical outcomes and assess Kinetic and Kinematic characteristics between current design and new design of Vanguard High Flex Rotating Platform Knee Systems	Vanguard High Flex RP (New Design)	Vanguard High Flex RP (same as control from subgroup 2)	Historical/concurrent control	ROM, AKS, Survivorship and Fluoroscopic analysis, Gait lab analysis, patella clunk and crepitus.

*Japanese sites will include equal number of Healthy Knees for ROM, Kinetic and Kinematic analysis.

** Subgroup 4 will be initiated once the new design of Vanguard high flex RP is release.

The study will be conducted over a period of 12 to 15 years. Patients from subgroups 2 and 4 will be followed at immediate postop, 6 weeks, 6 months, 1 year, 3 years, 5 years, 7 years and 10 years.

PATIENT SELECTION

All subjects, regardless of sex, race, or geographic location, must fit into the scope of the Inclusion / Exclusion criteria to be eligible for the study. If required per applicable regulations, all participants must sign an Informed Consent to be enrolled into the study.

Inclusion Criteria

In accordance with Indications for Use for Vanguard Complete Knee System and Vanguard High Flex Rotating Platform Knee System specifically:

- Painful and disabled knee joint resulting from osteoarthritis, rheumatoid arthritis, traumatic arthritis where one or more compartments are involved.
- Correction of varus, valgus, or posttraumatic deformity.
- Correction or revision of unsuccessful osteotomy, or arthrodesis.

Patient selection factors to be considered also include:

- Need to obtain pain relief and improve function

- Ability and willingness of the patient to follow instructions, including control of weight and activity level
- A good nutritional state of the patient, and
- The patient must have reached full skeletal maturity

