Exclusion Criteria

In accordance with Absolute and Relative Contraindications for use for Vanguard Complete Knee System and Vanguard High Flex Rotating Platform Knee System.

Absolute contraindications include: infection, sepsis, osteomyelitis, and failure of a previous joint replacement.

Relative contraindications include:

- A. Uncooperative patient or patient with neurologic disorders who are incapable of following directions,
- B. Osteoporosis,
- C. Metabolic disorders which may impair bone formation,
- D. Osteomalacia,
- E. Distant foci of infections which may spread to the implant site,
- F. Rapid joint destruction, marked bone loss or bone resorption apparent on roentgenogram,
- G. Vascular insufficiency, muscular atrophy, neuromuscular disease,
- H. Incomplete or deficient soft tissue surrounding the knee.

ENDPOINTS

	SUBGROUP 2	SUBGROUP 4
PRIMARY ENDPOINTS*	Range of Motion at 1 yr postop. AKS at 1 year postop	Range of Motion at 1 yr postop. AKS at 1 year post op
SECONDARY ENDPOINTS	At all follow-up visits: Survivorship American Knee Society Score. Range of Motion Radiographic Assessment Patient Satisfaction – EQ5D Complications including revisions Patella Clunk and Crepitus	At all follow-up visits: Survivorship American Knee Society Score. Range of Motion Radiographic Assessment Patient Satisfaction – EQ5D - OKS - FJS Complications including revisions Patella Clunk and Crepitus

*For sample size calculations.

PARTICIPANT POPULATION (SAMPLE SIZE)

Participant population is determined based on primary/secondary endpoints of each subgroup following superiority or non-inferiority methodologies. Minimum sample sizes are determined in order to prove the hypotheses.

Subgroup 2 - Primary Endpoint Range of Motion at 1 year postoperative
 Superiority test

Null Hypothesis: H_0 $\mu_t = \mu_c$

Alternative Hypothesis: H_a $\mu_t = \mu_c + d$

μ_t : mean of ROM in the trial group (Vanguard Complete Knee) at 1 year postoperative.

μ_c : mean of ROM in the control group (VG RP Knee) at 1 year postoperative.

$\alpha = 0.025$ Significance Level (95% confidence)

$\beta = 0.20$ 80% Power

$d = 5$ (degrees) Clinically Relevant Difference in ROM based on literature and engineering input.

$\xi = 17.5$ Estimate standard deviation of ROM at 1 year postoperative. This value is based on results (preop and 1 year postop) from literature¹

$N = 231$

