The following table summarizes data collection required during the course of the study.

SUBGROUP 2	PRE-OP	SURGERY	IMMEDIATE POST-OP	3 MO	6 MO	1 YR	3 YR	5 YR	7 YR	10 YR
Informed Consent	X									
Demographic	X									

and Historical Record											
Preoperative AKS	X										
Operative Record		X									
Immediate Post-Operative Radiographic Assessment (Bench Mark)			X								
Postoperative AKS (Including ROM)				X	X	X	X	X	X	X	X
Patella Clunk and Crepitus				X	X	X					
EQ5D				X	X	X	X	X	X	X	X
Radiographic Assessment				X	X	X	X	X	X	X	X
Complications & Revisions				Anytime							

SUBGROUP 4	PRE-OP	SURGERY	IMMEDIATE POST-OP	3 MO	6 MO	1 YR	3 YR	5 YR	7 YR	10 YR	
Informed Consent	X										
Demographic and Historical Record	X										
Preoperative AKS	X										
Operative Record		X									
Immediate Post-Operative Radiographic Assessment (Bench Mark)			X								
Postoperative AKS (Including ROM)				X	X	X	X	X	X	X	
Patella Clunk and Crepitus				X	X	X	X	X	X	X	
EQ5D/SF36				X	X	X	X	X	X	X	
Radiographic Assessment				X	X	X	X	X	X	X	
Complications & Revisions				Anytime							

PARTICIPANT EVALUATION SCHEDULES

All study Participants are expected to return for clinical, kinetic and kinematic analysis if any and radiographic evaluation at specific follow-up intervals. The following table summarizes the schedule for post-operative follow-up time intervals:

Evaluation Schedule		
Interval	Follow-Up Window	Months Post-Op Range
Immediate Post-Op	± 2 weeks	Immediate post-op < 2 weeks
3 month follow-up	± 1 month	2-4
6 month follow-up	± 1 month	5-7
1 year follow-up	± 2 months	10-14
3 year follow-up	± 3 months	33-39
5 year follow-up	± 3 months	57-63
7 year follow-up	± 3 months	81-87
10 year follow-up	± 3 months	117 - 123

COMPLICATIONS (ADVERSE EVENTS)

All adverse events, device related (see *Risk Analysis Section*) or non-device related, are to be recorded. Anticipated adverse events are defined, but not limited to, the following:

- Operative side knee manipulations or injections
- Operative side dislocations
- Operative side aspiration of joint fluids
- Falls
- Accidents- motor vehicle, motorcycle, ATV, etc.
- Death
- Any event in which the subject requires hospitalization or outpatient medical attention, including but not limited to: myocardial infarction, cerebral vascular accident, pulmonary emboli, gastrointestinal disorders, or a new diagnosis of a chronic condition (lung disease, renal disease, cancer, diabetes mellitus, hematological abnormalities, etc.).

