RADIOGRAPHIC PROTOCOL

1. **Radiographic Views**
The study requires a standard anteroposterior view, mediolateral view, and a skyline patellar view.
2. **Reviewer**
The study investigator will assess his own patient's radiographs.

3. Assessment Procedure

- Assessments will be recorded on the following two radiographic assessment reports:
 - Form XR100 (immediate post-operative)
 - Form XR200 (6 week, 6 month, 1 year, 3 year, 5 year, 7 year and 10 year).
- The radiographic films will be marked for measurements as described in the following “Measurement angles and reference points” section of this document. These “marked” radiographs will be used to determine the implant femoral flexion angle (α), tibial angle (β), total valgus angle (Ω), tibial angle (σ), and femoral flexion (γ).
- The immediate post-operative film will be used as an index for subsequent follow-up assessments.

The radiographic assessment definitions are as follows:

- Anteroposterior Radiograph:
This radiographic view can be obtained with the participant in the standing or recumbent position.
- Mediolateral Radiograph:
This radiographic view can be obtained with the participant in the standing or recumbent position.
- Skyline Radiograph:
This radiograph view can be obtained with the patello-femoral joint in flexion
- Radiolucency or Radiolucent Lines:
A radiographic clearing or line not exceeding 2mm in width at the bone/cement or cement/implant interface
- Osteolysis:
A progressive radiolucency > 2mm in **two or more** zones not present on immediate postoperative radiographs and/or a bony destructive lesion that is progressive in nature.
- Migration/Subsidence:
A component migration of > 3 mm or > 3° as compared to immediate post-operative radiographs is considered a failure.

DATA COLLECTION

All sites will be required to complete and submit case report forms on Biomet’s online database, Joint Assist 2.0, in a timely manner. Forms will be monitored for completeness and accuracy.

Further, it is imperative that the investigator answers all questions on the case report forms. All data should be accurate, indelible, legible, dated on the date of entry, and signed by initials, and/or formal signature by the authorized personnel documenting the data.

MONITORING PLAN

Prior to commencing the study the Monitor will provide the investigators with the necessary information to enable him/her to carry out his responsibilities. This information includes but not limited to:

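### The secondary endpoint list and the data collection tables disagree on patella clunk/crepitus timing in subgroup 2 and on the questionnaires in subgroup 4

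*Combined protocol and SAP*

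**What the plan says.** ENDPOINTS puts the secondary endpoints of both subgroups under the line "At all follow-up visits". The subgroup 2 list ends "Patient Satisfaction – EQ5D Complications including revisions Patella Clunk and Crepitus". The subgroup 4 list ends "Patient Satisfaction – EQ5D - OKS - FJS Complications including revisions Patella Clunk and Crepitus". So clunk/crepitus is due at every follow-up visit in both subgroups, and OKS and FJS are due at every follow-up visit in subgroup 4 only.

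PARTICIPANT DATA MANAGEMENT introduces its tables with "The following table summarizes data collection required during the course of the study". In the subgroup 2 table the row "Patella Clunk and Crepitus" carries three marks; in the subgroup 4 table the same row carries seven. The subgroup 4 table has one questionnaire row, EQ5D/SF36, and no row for OKS or FJS.

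The STUDY DESIGN table makes the High Flex RP control of subgroup 2 the control for subgroup 4 as well, and names clunk and crepitus among the subgroup 4 endpoints.

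The visit lists also differ. The text of STUDY DESIGN has patients "followed at immediate postop, 6 weeks, 6 months, 1 year, 3 years, 5 years, 7 years and 10 years", and RADIOGRAPHIC PROTOCOL has "Form XR200 (6 week, 6 month, 1 year, 3 year, 5 year, 7 year and 10 year". Both collection tables and PARTICIPANT EVALUATION SCHEDULES instead begin, after the immediate post-operative visit, with a "3 month follow-up".

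**The concern.** One part of the protocol defines what is to be measured and when. Another, presented as the required data collection, tells sites something different. A site working from the subgroup 2 table has no prompt to check for clunk or crepitus after the third marked visit.

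This matters most for the High Flex RP arm, because it serves twice: in the randomised comparison of subgroup 2, and as the historical or concurrent control for the new design. If the tables are followed, the new design is assessed on schedule out to 10 years while its control is not. The late part of a named subgroup 4 endpoint would then have no comparable control values. Late visits cannot be repeated once their window (±3 months from year 3 onward) has closed.

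For the questionnaires, OKS and FJS could go uncollected in subgroup 4. Even if they are collected, the control has no planned values to set against them.

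**Working it through.** There is no stated figure to reproduce. The check sets the endpoint list beside the tables and counts marks. Both table headers name seven visits after the immediate post-operative one: 3 months, 6 months, and 1, 3, 5, 7 and 10 years.

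| Item | ENDPOINTS | Collection table |
|---|---|---|
| Clunk/crepitus, subgroup 2 | every follow-up visit | 3 of 7 named visits |
| Clunk/crepitus, subgroup 4 | every follow-up visit | 7 of 7 |
| EQ5D, subgroup 4 | every follow-up visit | 7 of 7 (row shared with SF36) |
| OKS and FJS, subgroup 4 | every follow-up visit | no row |
| SF36, subgroup 4 | not listed | 7 of 7 (row shared with EQ5D) |
| OKS and FJS, subgroup 2 | not listed | no row |

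**Clunk/crepitus.** As extracted, the three subgroup 2 marks fall at 3 months, 6 months and 1 year, leaving 7 − 3 = 4 visits unmarked (3, 5, 7 and 10 years). PARTICIPANT POPULATION (SAMPLE SIZE) sets 250 knees per arm. Unmarked assessments before any loss to follow-up:

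- High Flex RP control: 250 × 4 = 1,000
- Both randomised arms: 500 × 4 = 2,000

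**Column alignment.** The subgroup 2 rows for AKS, EQ5D and radiographs each carry eight marks under seven named visits, so the exact position of the three clunk/crepitus marks is not certain. The mismatch does not depend on it: in the same table, neighbouring rows are marked throughout and this one has three marks at the early end.

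**Questionnaires.** Of the three instruments listed for subgroup 4 (EQ5D, OKS, FJS), two have no row. One instrument with a row (SF36) is not listed. OKS and FJS appear nowhere else in the document. Collecting both at seven visits would mean 2 × 7 = 14 forms per new-design knee.

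**Visit names.** STUDY DESIGN and RADIOGRAPHIC PROTOCOL each list seven visits after immediate post-op, starting at 6 weeks. The tables and the evaluation schedule list seven, starting at 3 months. One visit is exchanged for another; the count is the same.

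**The case against.** The strongest objection is that the short clunk/crepitus row may be deliberate. It alone stops early beside fully marked rows, and the STUDY DESIGN table gives only ROM and AKS for subgroup 2, naming clunk/crepitus only for subgroup 4. On that view ENDPOINTS is what needs correcting. This stands in part: the documents do not show which version was intended, so either direction of repair is open. It does not remove the contradiction, and a deliberate early stop would still leave the subgroup 4 comparison without scheduled late control data.

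It can also be said that only secondary endpoints are involved, that subgroup 4 has not started and its section must be completed anyway, and that complications may be recorded at any time. The first two are true and limit the weight. The third helps only partly: event reporting may catch symptomatic cases, but it is not a scheduled check at each visit.

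The stated harm concerns the control arm. Half of the 2,000 unmarked assessments are in the Complete Knee arm, which is not the subgroup 4 control.

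Some stronger readings are tempting but not supported:

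- **An eighth visit.** From the extra mark in some subgroup 2 rows a reader might infer a visit missing from the header, so that the clunk/crepitus marks end at 6 months and five visits are unmarked. No visit list has eight visits after immediate post-op. In the subgroup 4 table the spare cell is an empty one after 10 years, which points to a stray trailing column.
- **Scaling by retention.** A reader might shrink the counts by 231/250. The protocol states no loss rate; the ratio is only inferred from a 1-year sample size and says nothing about years 3 to 10.
- **Certain loss of data.** The case report forms are not in the documents, so the data could be missed; it cannot be said that they would be.
- **An error in the subgroup 2 questionnaire row.** There is none: ENDPOINTS lists only EQ5D there.

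**Conclusion.** The contradiction is real and should be resolved, on two counts. First, clunk/crepitus is listed for every follow-up visit in both subgroups but marked at three of seven in the subgroup 2 table, against seven of seven in subgroup 4. Following the tables leaves up to 1,000 late assessments unscheduled in the shared control, for an endpoint that STUDY DESIGN names for subgroup 4. Second, OKS and FJS are listed for subgroup 4 without a row in its table, SF36 has a row without being listed, and the control has no planned OKS or FJS.

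The primary endpoints, ROM and AKS at 1 year, are untouched. The count of 1,000 assumes 250 control knees, seven follow-up visits, the marks as extracted and no loss to follow-up. The existence of the mismatch needs none of these.

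**What to change.** Make one amendment that brings ENDPOINTS and the collection tables into agreement.

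1. **Visits.** Settle the 6-week/3-month mismatch across STUDY DESIGN, RADIOGRAPHIC PROTOCOL, the tables and the evaluation schedule, and confirm the columns of the subgroup 2 table.
2. **Clunk/crepitus.** Mark the remaining visits in the subgroup 2 table, at least for the High Flex RP control: up to 1,000 added checks, at visits already marked for AKS and radiographs. Using the same schedule in both randomised arms (up to 2,000) keeps the subgroup 2 comparison balanced and matches ENDPOINTS. If the sponsor prefers the shorter schedule, or where late control visits have already passed, limit the endpoint and the subgroup 4 comparison to visits assessed in both groups.
3. **Questionnaires.** Either add OKS and FJS rows to the subgroup 4 table and state that they are descriptive unless also collected in the control, or drop them from the list. Either list SF36 as an endpoint or remove it from the table.

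The cost is extra checks or forms, or else a narrower late comparison. If OKS and FJS are kept, the total at 14 forms per new-design knee depends on the subgroup 4 sample size, which the protocol leaves open. Control visits already past cannot be recovered, and the documents do not say how far subgroup 2 follow-up has gone.

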Vanguard High Flex RP knee is an extension to the existing Vanguard Knee and has been specifically designed to facilitate greater than 135 degrees of knee flexion as required by certain patients. Specifically the Vanguard High-Flex Knee components are required to be able to flex to 150° without point loading or falling off the back of the tibia and to be hyper extended to 15°. It should be noted that this range of motion would only be obtained where the patient had similar flexion and hyperextension ability prior to the arthroplasty. The decision on which rotating platform variant to use is at the discretion of the operating surgeon

Mobile bearing knees are considered advantages as they enable improved congruency between the femoral component and the bearing, compared with a fixed bearing, which results in lower contact stresses of the bearing, thereby reducing wear. Another advantage of mobile bearings is the ability for self-alignment, which reduces wear caused by mal-alignment, enabling the knee to function more naturally and prevents torsion stress on the implant/bone cement/bone interface which may cause loosening.

The tibial tray of the High Flex knee is available in 9 sizes, from 59 to 91mm in 4 mm increments, in interkok finish for cemented applications or with porous plasma sprayed titanium coating for cementless use. It is manufactured from cast cobalt chromium alloy. The stem has a tapered cone geometry for press fit stability. In the cementless option the proximal 1/3 of the stem is porous coated with plasma sprayed titanium. (Note: The tibial trays are manufactured and CE marked by Biomet Spain).

The femoral component is offered in thirteen sizes from 55 to 80mm in 2.5 mm increment, it is anatomic in design (i.e. right and left). It is manufactured from cast cobalt chromium alloy.

The bearing is compression moulded UHMPWE (ArCom). It is matched to the femoral component and is available in 5 thickness from 10-18mm (2mm increments) and 13 sizes from 50mm to 80mm (2.5mm increments). The bearing was designed specifically for the High-Flex to allow rotation of ±8° without overhang.

The patella has an anatomic design and is matched to the thirteen sizes of femoral component patella tracks. It is available in one thickness only. It is compression moulded from UHMWPE (ArCom). Use of the patella button is optional at the discretion of the surgeon.

STUDY DESIGN

[figure not shown]

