Consider lost to follow-up at 1 year postop, therefore the adjusted sample size is set as **250 knees per group (a total of 500 knees)**.

Subgroup 2 - Secondary Endpoint AKS at 1 year postoperative
 Non-inferiority test

Null Hypothesis: H_0 $\mu_t = \mu_c$

Alternative Hypothesis: H_a $\mu_t = \mu_c + d$

μ_t : mean of AKS score in the trial group (Vanguard Complete Knee) at 1 year postoperative.

μ_c : mean of AKS score the control group (VG RP Knee) at 1 year postoperative.

¹ [Miner AL](#), [Lingard EA](#), [Wright EA](#), [Sledge CB](#), [Katz JN](#); Knee range of motion after total knee arthroplasty: how important is this as an outcome measure, *J Arthroplasty*. 2003 Apr;18(3):286-94.

$\alpha = 0.025$	Significance Level (95% confidence)
$\beta = 0.10$	80% Power
$Z_{1-\alpha/2} = 1.96$	
$Z_{1-\beta} = 1.28$	
$d = 10$ points	Clinically Relevant Difference in Pain.
$\xi = 15$	Estimate standard deviation of AKS at 1 year postoperative. This value has been based on results from Biomet studies
$N = 48$	
	Consider possible lost to follow-up at 1 year postop, therefore the adjusted sample size is set as 51 knees per group. The final sample size for subgroup 2 is larger of the two sample sizes: 250 knees per group.
	Therefore there will be 250 Vanguard Complete Knee will be compared to 250 Vanguard High Flex RP knee for subgroup 2 study.
	Due to unknown release schedule for new designed VG High Flex RP Knee, sample size of subgroup 4 will be determined at time of the product release. Nevertheless the sample size will be determined based on the comparison to results of 250 VG High Flex RP knee of current design from subgroup 2.

RANDOMIZATION

For subgroup 2 study, patients will be randomized to receive Vanguard Complete Knee (trial group), or Vanguard High Flex RP Knee (control group). Patients have an equal opportunity of being assigned to the trial group or control group. The randomization will occur via a random number generator (manual or computer). The doctor or other health care professional does not choose the participants for each group. For Patients satisfying inclusion criteria, randomization will occur by retrieving the next randomly generated group assignment.

INSTITUTIONS

There will be a maximum of 8 sites from Korea and Japan in subgroup 2. The number of sites for subgroup 4 will be determined once new design of Vanguard High Flex RP is released.

PARTICIPANT DATA MANAGEMENT

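### Subgroup 2: 1-year ROM and AKS are compared with no baseline term although a pre-op AKS is scheduled; adjusting would add precision at almost no cost

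*Combined protocol and SAP*

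**What the plan says.** The Participant Population (Sample Size) section gives the only statement of how subgroup 2 will be compared. For range of motion (ROM), the trial-arm quantity is the "mean of ROM in the trial group (Vanguard Complete Knee) at 1 year postoperative", set against the same mean in the control arm. For AKS it is the "mean of AKS score in the trial group (Vanguard Complete Knee) at 1 year postoperative", again against the control mean. The ROM calculation uses a standard deviation of 17.5, labelled "Estimate standard deviation of ROM at 1 year postoperative". The AKS calculation uses 15, also described as a 1-year SD.

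No covariate, change score or model appears there, and the document has no separate analysis section.

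The subgroup 2 table under Participant Data Management schedules "Preoperative AKS" at the pre-op visit. The row for the post-operative AKS notes that ROM is part of it. The pre-op row carries no such note.

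Under Device Description, the text on the High Flex knee says that "this range of motion would only be obtained where the patient had similar flexion and hyperextension ability prior to the arthroplasty".

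**The concern.** When a baseline measurement of the outcome exists, a linear model with treatment and that baseline estimates the same difference in means as the raw comparison. Its residual SD is smaller whenever baseline and outcome are correlated. A plan that collects the baseline and does not use it gives up precision. This matters most for ROM, which sets the 250 knees per group and has the least spare power. Because no model is written down, the decision to adjust could also be taken after the results are seen; naming the covariate now closes that choice.

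**Working it through.** **Inputs from the sample-size section.** ROM: difference 5 degrees, SD 17.5, alpha 0.025 (labelled as 95% confidence, sidedness not stated), power 80%, N = 231 per group. AKS: difference 10 points, SD 15, z values 1.96 and 1.28, N = 48 per group. The correlation r between the pre-op covariate and the 1-year value is not in the documents and is assumed throughout.

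**Step 1: reproduce the plan's sizes without a baseline term.** N per group = 2(z_alpha + z_beta)² SD² / d².

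- ROM, two-sided 0.025: 2 × (2.2414 + 0.8416)² × 17.5² / 5² = 232.9, so 233. This is close to the stated 231 but not exact.
- ROM, two-sided 0.05: 2 × (1.96 + 0.8416)² × 17.5² / 5² = 192.3, so 193.
- AKS: 2 × (1.96 + 1.28)² × 15² / 10² = 47.2, so 48, as stated.

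Both stated sizes are thus consistent with unadjusted comparisons of 1-year values. Because the alpha label is ambiguous, ROM power is shown below under both readings.

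**Step 2: ROM with a baseline covariate at 231 per group.** Residual SD = 17.5 × √(1 − r²). Power = Φ(5 / (SD × √(2/231)) − z). The 95% half-width is 1.96 × SD × √(2/231), with √(2/231) = 0.09305.

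| Assumed r | Residual SD | Power, two-sided 0.025 | Power, two-sided 0.05 | 95% half-width (degrees) |
|---|---|---|---|---|
| none (unadjusted) | 17.50 | 79.7% | 86.7% | 3.19 |
| 0.1 | 17.41 | 80.1% | 87.0% | 3.18 |
| 0.3 | 16.69 | 83.6% | 89.6% | 3.04 |
| 0.5 | 15.16 | 90.4% | 94.4% | 2.76 |

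The rows for r = 0.3 and 0.5 are the assumed range for pre-op ROM as covariate. If only pre-op AKS is available, its correlation with 1-year ROM is unknown and probably lower. At an assumed r of 0.1 to 0.3, power is 80.1%-83.6% or 87.0%-89.6%, so the gain may be close to nil.

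**Step 3: AKS at the same 231 per group.**

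- Unadjusted: 10 / (15 × 0.09305) = 7.16. Less 1.96 this is 5.20, so power exceeds 99.99% before any adjustment.
- Half-width, 1.96 × 15 × √(1 − r²) × 0.09305: 2.74 unadjusted, 2.61 at r = 0.3, 2.37 at r = 0.5.

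**The case against.** The strongest reply is that nothing here is wrong. Subgroup 2 is randomised, and "Patients have an equal opportunity of being assigned to the trial group or control group", so the raw comparison of means is unbiased. Sizing without a covariate is ordinary conservative practice, and the hypotheses as written are equally compatible with an adjusted analysis. The benefit is also least certain where it would count: AKS has a scheduled baseline but needs no more power, while ROM would gain but its baseline is not confirmed as recorded. All of this stands, and it limits the point to an efficiency gain.

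Four stronger readings are tempting, and the documents do not support them:

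- **The plan rejects adjustment.** It does not. It leaves the model unspecified.
- **The trial is underpowered or its result would be biased.** Unadjusted power at 231 is 79.7% or 86.7%, at or near the stated 80%, and randomisation protects against bias.
- **The plan itself treats pre-op motion as prognostic for the endpoint.** The Device Description sentence concerns reaching the High Flex design range (150 degrees of flexion, 15 of hyperextension). It does not speak of mean 1-year ROM in both arms, or of AKS. It makes a correlation plausible but gives no size.
- **The ROM SD already reflects baseline.** The note "This value is based on results (preop and 1 year postop) from literature" describes the source of the 17.5. The figure itself is labelled as the SD at 1 year.

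What survives the reply is that a baseline already scheduled goes unused in the stated comparisons. Including it costs one degree of freedom, which is negligible at this size even if the correlation turns out to be low.

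**Conclusion.** The point holds as a recommended improvement. It does not show the planned comparison or its sample size to be invalid.

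With pre-op ROM as covariate and r between 0.3 and 0.5, ROM power would rise from 80% to 84%-90% (two-sided 0.025) or from 87% to 90%-94% (two-sided 0.05), with an interval about 5% to 13% narrower (3.04/3.19 and 2.76/3.19). That rests on the assumed correlation, on 17.5 being the 1-year SD as labelled, on 231 evaluable knees per group, and on pre-op ROM being recorded. Without pre-op ROM, the gain for ROM could be negligible. For AKS the baseline is certainly scheduled, but the benefit is confined to a modestly narrower interval, well inside the 10-point difference either way.

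**What to change.** 1. Specify the main analysis of 1-year AKS in subgroup 2 as a linear model with treatment and pre-op AKS, reporting the adjusted difference in means and its confidence interval.
2. Check whether the pre-op AKS form records ROM. If it does, say so in the data-collection table and analyse 1-year ROM with treatment and pre-op ROM. If it does not, use pre-op AKS and accept that the gain is unknown and probably smaller.
3. State a rule for missing pre-op values that does not depend on treatment, for example imputing the overall mean.

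The cost is a few sentences and one check of a form. The change needs no added visit and no change to the sample size, and the quantity estimated remains the difference in 1-year means.

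### Subgroup 2 sample-size blocks contradict themselves: the AKS inputs give 90% power but are labelled 80%, and the ROM figure of 231 per group does not follow at 95% confidence (193)

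*Combined protocol and SAP*

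**What the plan says.** All of this is in the section on participant population (sample size), with one cross-reference to the ENDPOINTS table.

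- **ROM at 1 year (superiority).** The block prints "\alpha = 0.025$ Significance Level (95% confidence" and "\beta = 0.20$ 80% Power", with d = 5 degrees, SD = 17.5 and N = 231. It prints no z value and does not say whether alpha is one- or two-sided. The alternative is written as a single shift: "Alternative Hypothesis: H_a $\mu_t = \mu_c + d".
- **Loss adjustment for ROM.** After 231, the text continues: "Consider lost to follow-up at 1 year postop, therefore the adjusted sample size is set as" 250 knees per group. No loss rate is given.
- **AKS at 1 year (non-inferiority).** The block prints the same alpha and the same 95% confidence label, then "Z_{1-\alpha/2} = 1.96". Beta is 0.10, on a row labelled 80% power. The z value for beta is 1.28, d = 10 points, SD = 15 and N = 48, raised to 51 for losses.
- **Choice of size.** "The final sample size for subgroup 2 is larger of the two sample sizes: 250 knees per group".
- **Status of AKS.** The sample-size block is headed "Subgroup 2 - Secondary Endpoint AKS at 1 year postoperative", whereas the primary row of the ENDPOINTS table lists "Range of Motion at 1 yr postop. AKS at 1 year postop".

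**The concern.** Within the AKS block, beta = 0.10 and a label of 80% power cannot both be right. The printed subscript is also at odds with the printed alpha: for alpha = 0.025, 1.96 is the 1-alpha quantile, and the 1-alpha/2 quantile is 2.241.

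Across the two blocks, one alpha line appears to stand for two critical values. AKS uses 1.96. The ROM figure of 231 is close only to what 2.241 would give.

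This matters because ROM sets the size of the study. Without a stated loss rate, the number of evaluable knees needed at 1 year is the only benchmark for attrition, and it differs by 40 per group (233 - 193) between the two readings. The threshold for the 1-year ROM test is unsettled for the same reason. Subgroup 4 is to be sized later against the 250 High Flex RP knees of Subgroup 2, so the ambiguity could carry forward.

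**Working it through.** Formula for two means with equal allocation: n per group = 2 x (z_alpha + z_beta)^2 x (SD/d)^2. For the AKS non-inferiority test with a true difference of zero and a margin of 10, the expression is the same. Inputs are those printed in the two blocks. Quantiles: 1.960 (one-sided 0.025 or two-sided 0.05), 2.2414 (two-sided 0.025), 0.8416 (80% power), 1.2816 (90% power).

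**AKS** (SD 15, d 10; 2 x (15/10)^2 = 4.5)

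- Printed z values: (1.96 + 1.28)^2 x 4.5 = 47.2, so 48. This reproduces the plan's figure at 90% power.
- 80% power, z = 1.96: (1.960 + 0.8416)^2 x 4.5 = 35.3, so 36.
- Two-sided 0.025: 43 at 80% power; (2.2414 + 1.2816)^2 x 4.5 = 55.9, so 56, at 90% power. Neither is 48.
- Power with 48 per group: 90.4% at z = 1.96 and 84.7% at z = 2.241.

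Beta, its z value and N therefore agree with each other, and the 80% label is the odd one out.

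**ROM** (SD 17.5, d 5; 2 x (17.5/5)^2 = 24.5)

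- z = 1.96, 80% power: (1.960 + 0.8416)^2 x 24.5 = 192.3, so 193. The plan prints 231, which is 38 more.
- Two-sided 0.025, 80% power: (2.2414 + 0.8416)^2 x 24.5 = 232.9, so 233. This is two knees from 231.
- Other readings: one-sided 0.05 gives 152; two-sided 0.05 with 90% power gives 258.
- A t-test calculation gives 193.3 and 234.1 for the first two readings, so the normal approximation does not explain the gap.

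**ROM power** = Phi(d / (SD x sqrt(2/n)) - z_alpha)

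- n = 231: Phi(3.071 - 1.960) = 86.7%; Phi(3.071 - 2.2414) = 79.7%.
- n = 250: Phi(3.194 - 1.960) = 89.1%; Phi(3.194 - 2.2414) = 83.0%.

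**AKS power at 250 per group** exceeds 99.9% with either z.

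**Loss from 250 that still leaves 80% ROM power**

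- If 193 are needed: 1 - 193/250 = 22.8%.
- If 233 are needed: 1 - 233/250 = 6.8%.
- The plan's own step from 231 to 250 implies 1 - 231/250 = 7.6%.

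**The case against.** The strongest reply is that the ROM figure is nearly right. Take alpha = 0.025 literally, apply the 1-alpha/2 subscript that the AKS block prints, and the result is 233. The printed 231 is within 1% of that and has 79.7% power. On this reading only the 95% confidence label is wrong for ROM, apart from a two-knee gap. That stands, so it would be too strong to say that 231 cannot be obtained on any reading. But this reading conflicts with the 95% label in both blocks and with the 1.96 that AKS uses under the same alpha, so a conflict remains either way.

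A second reply is that the AKS alpha line is only loose notation for 0.025 per tail. That is fair: a one-sided 0.025 with Z(1-alpha) and a two-sided 0.05 with Z(1-alpha/2) give the same N. It does not rescue the power label.

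A third reply is that nothing changes in practice, because 250 per group is enough. This stands for enrolment before losses. It does not settle the attrition benchmark or the test threshold.

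Three further inferences are tempting but unsupported:

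- **That 231 is 193 already raised for losses.** No rate is printed, and the text applies its loss adjustment after 231, to reach 250.
- **That 0.025 is 0.05 split over two primary endpoints.** No multiplicity rule is stated, and the sample-size block calls AKS secondary.
- **That every slip errs on the safe side.** With z = 2.241, 231 falls just short of 80% power for ROM, and 48 gives 84.7% for AKS, below the 90% implied by its beta. Only the final 250 is adequate on both readings.

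**Conclusion.** The point holds as a contradiction among printed figures and should be corrected. The AKS power label is wrong for the beta, z value and N beside it, and the AKS subscript does not fit its alpha. For ROM, 231 does not follow at 95% confidence, where 193 per group suffice. It comes close only at 97.5% confidence, where 233 are needed.

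The effect on enrolment is nil. A reader might infer that Subgroup 2 is underpowered; the plan's figures do not support that, since 250 per group gives 89.1% or 83.0% ROM power before losses. The real uncertainty is the tolerable 1-year loss, 22.8% against 6.8%, and which threshold the ROM test will use.

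These results rest on the printed SDs and differences, equal allocation, equal loss in both groups and knees counted as independent observations. The documents do not show which alpha was intended.

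**What to change.** State alpha and its sidedness once and use the same z value in both blocks, unless different levels are intended and said to be so. Then follow one of two routes:

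- **If z = 1.96 applies.** Change the AKS label to 90% power and keep N = 48. Write either a one-sided alpha of 0.025 with Z(1-alpha) or a two-sided alpha of 0.05 with Z(1-alpha/2). For ROM, print z = 1.96 and restate the requirement as 193 per group for 80% power, noting that 231 evaluable knees give about 87% and 250 about 89%.
- **If a two-sided 0.025 is intended.** Change 95% confidence to 97.5%, print z = 2.241 and give ROM N = 233, noting that 250 gives 83.0%. If this level also covers AKS, print z = 2.241 there, N = 56 and 90% power. If it does not, the AKS power label still needs correcting to 90%.

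Separately, make the status of AKS the same in the ENDPOINTS table and the sample-size heading, whichever is meant.

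The cost is protocol wording only. Enrolment stays at 250 knees per group on either route. The change should be made before the 1-year ROM analysis.
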